### 8.2.6 Solicited AE

After each vaccination subjects receive a memory aid to record solicited local and general AEs most likely to occur on the day of vaccination and the following 7 days (Days 0-7, 8 day period).

All solicited symptoms observed after vaccination with details concerning the intensity and the course of the reaction should be documented there. The investigator will collect this

information during the following scheduled visits and transfer it to the eCRF. Local and general reactions still ongoing after 7 days will be measured or examined each day until resolution or until no further change can reasonably be expected, and the last day of symptoms and maximum intensity will be documented in the memory aid.

In case of severe and unexpected local and/or general reactions, the subject should be instructed to contact the trial physician outside of scheduled trial visits.

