**Visit 2 (Visit 1 + 12–16 days)**

**The following tasks will be performed:**

- Targeted physical examination including auscultation of the heart and lungs
- Evaluation of vital signs
- Examination of the injection site
- Performing ECG
- Collection of the memory aid handed out at Visit 1, review with subject
- Blood draw for safety laboratory ( 11 ml) including troponin I
- Recording of AEs/SAEs/AESI and concomitant medication

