**Visit 3 (Visit 1 + 28–35 days)**

**Tasks to be performed prior to vaccination:**

- Check withdrawal criteria
- Targeted physical examination including auscultation of the heart and lungs
- Evaluation of vital signs
- Counseling on avoidance of becoming pregnant: Review of acceptable contraceptive methods and recent menstrual history with WOCBP
- Urine pregnancy test (WOCBP only)
- Recording of AEs/SAEs/AESIs and concomitant medications

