**4.2.3 Follow-Up (FU) Phase**

To monitor long-term safety, the CTS will contact the subject by phone to inquire whether an SAE /AESI might have occurred since the last trial visit and if there is any new information on SAEs/AESIs/AEs ongoing at last trial visit. In cases where a serious condition is detected, the trial subject will be requested to return for a physical examination and further work-up at the CTS.

For subjects who were withdrawn from the 2nd vaccination, the FU visit will be performed 6 months after the 1st vaccination (see section 4.2.5. withdrawal from 2nd vaccination).

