##### 8.1.3.1 Unsolicited AE

Unsolicited AEs are defined as any untoward (undesirable) occurrence of a medical event in a clinical trial subject temporally associated with the administration of an IMP or a medical

product (MP) which does not necessarily have a causal relationship with this IMP/MP. Up to Visit 5 all AEs (e.g. feeling of ill-health, subjective symptoms and objective signs, intercurrent diseases, accidents, etc.) observed by the investigator and/or reported by the subject must be recorded in the eCRF and in the subject's medical record regardless of the assessment of causality in relationship with the IMP/MP.

Abnormal laboratory values assessed as being clinically significant by the investigator are to be documented as AEs. In addition, abnormal laboratory values fulfilling the Grade 3 or Grade 4 criterion according to the toxicity scale (see [Appendix I](#)) are to be documented as AE in the eCRF and in the subject's medical record, regardless of whether they are considered clinically relevant or not. Toxicity grade and seriousness of an AE will be assessed separately, i.e. a Grade 3 or Grade 4 AE will not automatically be regarded as serious.

The investigator should ask the subject if they have experienced any AEs since their last visit. All intercurrent diseases reported by the subject, need to be recorded by the investigator in the appropriate page of the eCRF and in the subject's medical record.

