#### **8.1.3.2 Solicited AE**

Within this clinical trial protocol solicited AEs are defined as all symptoms specifically listed in the memory aid provided to the subjects following each vaccination. The subjects are requested to monitor and record local symptoms in the memory aid, i.e. erythema, swelling, induration, pruritus and pain at the site of injection as well as general symptoms, i.e. body temperature, headache, chills, myalgia, nausea and fatigue daily for the day of vaccination and the following 7 days (Days 0-7, 8 day duration).

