#### Troponin I

Troponin I will be measured at the SCR and at Visit 2. At Visit 4 troponin I measurement is only done if clinically indicated.

[figure not shown]
Cardiac events fulfill the definition of an AESI as described under [section 8.1.3.3](#). The investigator will be asked to assess the clinical significance of the case.

Case definitions as published by the Centers of Disease Control and Prevention ("Update: Cardiac-Related Events During the Civilian Smallpox Vaccination Program --- United States, MMWR May 30, 2003, Vol. 52, No. 21, p. 494") are provided in [Appendix II](#) in order to:

- help investigators to recognize possible events of acute myocarditis and/or pericarditis and
- distinguish from unspecific and isolated ECG changes without or with unclear clinical significance.

Subjects who develop any kind of cardiac signs or symptoms during the trial such as but not limited to chest pain, dyspnea, arrhythmia or edema are referred to a local cardiologist for cardiac evaluation such as (treadmill) ECG, cardiac enzymes and/or echocardiogram. Depending on the results of these evaluations, further diagnostic tests will be done as recommended by the cardiologist and subjects will be followed up at a frequency determined by the cardiologist. AESIs will be followed up until complete resolution or until the sequelae are stable and considered to be permanent.

[Figure 1](#) outlines the algorithm for assessment of cardiac events.

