## 17.2 Appendix II: Case Definitions Acute Myocarditis / Pericarditis

### Case Definition for Acute Myocarditis

A possible case of acute myocarditis is defined by the following criteria and the absence of evidence of any other likely cause of symptoms:

Presence of dyspnea, palpitations, or chest pain of probable cardiac origin in a subject with either one of the following:

- ECG abnormalities beyond normal variants, not documented previously, including
- ST-segment or T-wave abnormalities,
- Paroxysmal or sustained atrial or ventricular arrhythmias,
- AV nodal conduction delays or intraventricular conduction defects, or
- Continuous ambulatory electrocardiographic monitoring that detects frequent atrial or ventricular ectopy, **or**
- Evidence of focal or diffuse depressed left-ventricular (LV) function of indeterminate age identified by an imaging trial (e.g., echocardiography or radionuclide ventriculography).

A probable case of acute myocarditis, in addition to the above symptoms and in the absence of evidence of any other likely cause of symptoms, has one of the following:

- Elevated cardiac enzymes, specifically, abnormal levels of cardiac troponin I, troponin T, or creatine kinase myocardial band (a troponin test is preferred);
- Evidence of focal or diffuse depressed LV function identified by an imaging trial (e.g., echocardiography or radionuclide ventriculography) that is documented to be of new onset or of increased degree of severity (in the absence of a previous trial, findings of depressed LV function are considered of new onset if, on follow-up studies, these findings resolve, improve, or worsen); or
- Abnormal result of cardiac radionuclide imaging (e.g., cardiac magnetic resonance imaging with gadolinium or gallium-67 imaging) indicating myocardial inflammation.

A case of acute myocarditis is confirmed if histopathologic evidence of myocardial inflammation is found at endomyocardial biopsy or autopsy.

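### The instruction to contact the site covers a narrower set of events than the protocol's own cardiac AESI definition, so mild cardiac symptoms may wait for the next planned contact

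*Protocol*

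**What the plan says.** The secondary objectives in the synopsis (1.5) single out cardiac signs and symptoms that point to myo-/pericarditis. Section 8.1.3.3 makes any cardiac sign or symptom since the first vaccination an AESI, with no severity threshold. Section 8.2.7 starts its referral rule with "Subjects who develop any kind of cardiac signs or symptoms during the trial" and sends them to a local cardiologist.

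The routes by which a symptom reaches the site are these:

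- **Memory aid (8.1.3.2, 8.2.6).** It covers five injection-site symptoms and "general symptoms, i.e. body temperature, headache, chills, myalgia, nausea and fatigue daily for the day of vaccination and the following 7 days". No cardiac symptom is listed.
- **Contact between visits (8.2.6).** "In case of severe and unexpected local and/or general reactions, the subject should be instructed to contact the trial physician". The protocol contains no other instruction to call about symptoms.
- **Visits (8.1.3.1).** "The investigator should ask the subject if they have experienced any AEs since their last visit". The schedule (1.6) also lists AESI recording as a task.
- **Phone follow-up (4.2.3).** The site asks about SAEs and AESIs. On return to the site: "In cases where a serious condition is detected, the trial subject will be requested to return for a physical examination".

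ECG and troponin I are mandatory at screening and V2. At V4 they are done only if clinically indicated (1.6, 4.2.2, 8.2.7).

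**The concern.** The event the trial sets out to capture is any cardiac symptom. The threshold at which a subject is told to call is a severe and unexpected reaction. Mild chest pain or palpitations fall under the first and outside the second, and are not on the memory aid either.

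Timing can matter for classification. Appendix II counts symptoms as possible myocarditis only with further evidence, such as "ECG abnormalities beyond normal variants, not documented previously, including" specified findings, or depressed left-ventricular function on imaging. Probable myocarditis needs enzyme or imaging evidence. An episode reported late could be recorded as an AESI and still not be classifiable as a case.

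Section 9.3 draws its cardiac conclusions from 0, 1 or 2 observed cases and treats every true case as observed. If some are not, a low count looks more reassuring than it is, in every arm.

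**Working it through.** **1. Waiting times, from the visit windows in 1.6 and 4.2.2**

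Inputs: "Visit 2 (Visit 1 + 12–16 days"); "Visit 3 (Visit 1 + 28–35 days"); V4 at V3 + 12–16; V5 at V3 + 28–35; phone FU at V3 + 182–210.

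| Interval | Longest gap | Routine ECG and troponin I at its end |
|---|---|---|
| V1–V2 | 16 days | Yes |
| V2–V3 | 35 − 12 = 23 days | No |
| V3–V4 | 16 days | Only if clinically indicated |
| V4–V5 | 35 − 12 = 23 days | No |
| V5–phone FU | 210 − 28 = 182 days (shortest 182 − 35 = 147) | No |

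Onset before V2 therefore meets mandatory testing within 16 days without any call from the subject. After dose 2 no ECG or troponin I is mandatory. What remains is symptom reporting, vital signs and auscultation.

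**2. The plan's own figures in 9.3, reproduced (exact binomial)**

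- At least one case in 3,000 at a rate of 1/1,000: 1 − 0.999^3000 = 95.03% (stated 95%).
- At 5/100,000: at least one case in 3,000 is 13.93% (stated 13.9%), two or more is 1.02% (stated 1.02%), and at least one in 1,000 placebo subjects is 4.88% (stated 4.9%).

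The arithmetic is sound, and it takes every case as seen and classified.

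**3. Sensitivity to incomplete capture**

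Let s be the share of true cases that are seen and classified. The documents give no value for s, so the range below is assumed.

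- Zero cases in 3,000, one-sided 95% upper bound on the true rate: (1 − 0.05^(1/3000)) / s = 0.000998 / s.
- Two or fewer cases when the true rate is 1/330: P(X ≤ 2), with X binomial (3,000, s/330).

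| s | Upper bound after zero cases | P(X ≤ 2) at a true rate of 1/330 |
|---|---|---|
| 1.0 | 1/1,002 | 0.6% |
| 0.9 | 1/902 | 1.2% |
| 0.8 | 1/802 | 2.4% |
| 0.7 | 1/701 | 4.7% |
| 0.6 | 1/601 | 9.1% |

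Setting the tail probability to 0.05 gives the value of s below which each statement against 1/330 fails: about 0.33 for zero cases, 0.52 for one case and 0.69 for two cases. The zero-case statement against 1/1,000 has almost no slack even at s = 1.

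**4. Follow-up wording side by side**

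Sections 4.2.3 and 1.6 (footnote 1) tie return to the site to a serious condition, and 8.2.3 to a potentially serious one. Section 8.2.7 ties cardiology referral to any cardiac sign or symptom during the trial, and by 4.3 the trial includes the phone follow-up. The two actions have different triggers, and the protocol does not say how they fit together for a mild cardiac symptom first reported by phone.

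**The case against.** The case for leaving the text alone is substantial.

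- **Inquiry is not purely general.** AESI recording is a listed task at V2 to V5 and at the phone call, and an AESI is by definition cardiac. Cardiac AESIs are also a withdrawal criterion checked before dose 2 (4.2.5). This stands, and it limits the problem to delay and to how the question is put.
- **There are other safeguards.** Every subject has ECG and troponin I at V2 and auscultation at every active-phase visit. Unscheduled visits and extra tests are allowed. This stands too, although an unscheduled visit needs the site to hear of the symptom.
- **The call instruction is not exclusive.** It sits in the reactogenicity section and does not discourage other calls. The memory aid, the consent form and Figure 1 are not available here. The point is only that the protocol states no other instruction.
- **Late reports can still be classified.** Possible pericarditis needs only typical chest pain without another likely cause. Possible myocarditis can rest on left-ventricular dysfunction of indeterminate age. Appendix II's remark that findings may resolve concerns left-ventricular imaging, not ECG or troponin.
- **The benchmark.** The 1/330 comparison derives from ten serious cases (2.3, 9.3), so missing mild, self-limited episodes weakens it less than the table suggests.
- **Capture values.** They are assumed and applied to all cases, although mainly mild episodes outside the V2 testing would be affected.

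A reader might infer that myo-/pericarditis will commonly go unnoticed for months, or that the diagnostic evidence will be gone. The documents support neither. Months apply only to onset after V5, at least 28 days after the last dose, and no time course for ECG or troponin changes is given. A reader might also call 4.2.3 and 8.2.7 a contradiction. They govern different actions, so it is a mismatch of triggers.

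**Conclusion.** The concern holds in limited form. The stated threshold for contacting the site is narrower than the protocol's AESI definition and its referral trigger, and the memory aid does not close the difference. The resulting delay is at most 23 days in the active phase and about five to six months only for onset after V5. The exposure is greatest after dose 2, when no routine ECG or troponin I backs up a missed or late report.

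The effect on the case count cannot be estimated from the documents. At an assumed 80% capture the zero-case bound moves from 1/1,002 to 1/802, while the two-case conclusion against 1/330 still holds; it fails only below about 69%. These figures assume a one-sided 0.05 level and the same capture for all cases. They show how sensitive 9.3 is to capture, not that capture is low. It would be wrong to conclude that any figure in 9.3 is miscalculated.

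This is a cheap improvement of low to moderate priority.

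**What to change.** 1. Reconcile the reporting instruction in 8.2.6 with the AESI definition in 8.1.3.3 and the referral trigger in 8.2.7, and carry the reconciled wording onto the memory aid.
2. Have the AESI inquiry at each visit and at the phone follow-up name the symptoms that 8.2.7 and Appendix II already list (chest pain, dyspnea, palpitations, arrhythmia, edema).
3. Reconcile the serious-condition wording in 4.2.3, 1.6 (footnote 1) and 8.2.3 with the any-cardiac-symptom wording in 8.2.7. If the triggers are to stay different, limit the case-count statements in 9.3 to the period up to V5. Which trigger applies is a clinical decision for the sponsor.

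The cost is protocol and memory-aid wording. The downside is somewhat more non-specific symptom reports in all arms, each entering the referral that 8.2.7 already requires.

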### **8.2.6.1 Solicited Local AE**

The solicited local symptoms erythema, swelling, induration, pruritus and pain at the injection site are to be documented in the memory aid by the subject.

To standardize procedures, uniform rulers will be handed out to all subjects for measurement of erythema, swelling and induration diameters, as will digital thermometers for oral measurements of body temperature.

#### Assessment of Intensity

Injection site erythema	size measured in diameter
Injection site swelling	size measured in diameter
Injection site induration	size measured in diameter

The maximum severity will be scored as follows:

0	=	0
1	=	< 30 mm
2	=	≥ 30 – <100 mm
3	=	≥ 100 mm

Injection site pruritus:

0	=	Absent
1	=	Mild
2	=	Moderate
3	=	Severe

Injection site pain:

0	=	Absent
1	=	Painful on touch
2	=	Painful when limb is moved
3	=	Spontaneously painful / prevents normal activity

### Assessment of Causality

Solicited local AEs are defined as being related to the trial vaccine.

#### **8.2.6.2 Solicited General AE**

The solicited general symptoms body temperature, headache, myalgia, nausea, chills and fatigue are to be documented in the memory aid by the subject.

### Assessment of Intensity

Subjects are asked to document the solicited general AEs in the memory aid as described in [Table 2](#) below. In the subject's memory aid, the grading of maximum symptom intensity is described in basic, easily understood language based on the following descriptions:

**Table 2: Grading of General Symptoms from the Subject's Memory Aid**

Medical Dictionary for Regulatory Activities (MedDRA) coded Preferred Term General AEs	Grade	Maximum Severity
Body temperature*	0	< 99.5°F (< 37.5°C)
	1	≥ 99.5 – < 100.4°F (≥ 37.5 – < 38.0°C)
	2	≥ 100.4 – < 102.2°F (≥ 38.0 – < 39.0°C)
	3	≥ 102.2 – < 104°F (≥ 39.0 – < 40.0°C)
	4	≥ 104°F (≥ 40.0°C)
Headache, Myalgia, Nausea, Chills and Fatigue	0	None
	1	Mild: easily tolerated, minimal discomfort and no interference with daily activity
	2	Moderate: Some interference with daily activity
	3	Severe: Prevents daily activity

\*Pyrexia is defined as oral temperature ≥ 100.4°F (≥ 38.0 C).

### Assessment of Causality

Causal relationship between solicited general AEs and the vaccine will be assessed by the investigator using the same categories as for unsolicited AEs (see section [8.2.5](#)).

#### **8.2.7 Cardiac Assessment**

To evaluate the cardiac profile of IMVAMUNE®, targeted physical exams including auscultation of the heart and lung will be performed. Any kind of cardiac signs (i.e. discovered by the physician during examination of the patient) or symptom(s) (i.e. experienced and reported by the patient) detected during the trial such as but not limited to chest pain, dyspnea, arrhythmia or edema are recorded.

### ECG

A standard 12-lead ECG will be taken at SCR and at Visit 2. At Visit 4 an ECG is only done

if clinically indicated. ECGs will be evaluated by central ECG reading. The workflow and communication flow will be provided in a separate manual.

#### Cardiac risk factors

The individual cardiac risk factor is calculated at SCR (for subjects 20 years of age and older), using the National Cholesterol Education Program's risk assessment tool (<http://hin.nhlbi.nih.gov/atp/iii/calculator.asp?usertype=prof>). Subjects with a ten percent or greater risk of developing a myocardial infarction or coronary death within the next 10 years are excluded from trial participation.

In addition, the family cardiac risk factor is evaluated at SCR. Subjects with an immediate family member (father, mother, brother, or sister) who has had onset of ischemic heart diseases before 50 years of age are also excluded from trial participation.

#### Troponin I

Troponin I will be measured at the SCR and at Visit 2. At Visit 4 troponin I measurement is only done if clinically indicated.

[figure not shown]
Cardiac events fulfill the definition of an AESI as described under [section 8.1.3.3](#). The investigator will be asked to assess the clinical significance of the case.

Case definitions as published by the Centers of Disease Control and Prevention ("Update: Cardiac-Related Events During the Civilian Smallpox Vaccination Program --- United States, MMWR May 30, 2003, Vol. 52, No. 21, p. 494") are provided in [Appendix II](#) in order to:

- help investigators to recognize possible events of acute myocarditis and/or pericarditis and
- distinguish from unspecific and isolated ECG changes without or with unclear clinical significance.

Subjects who develop any kind of cardiac signs or symptoms during the trial such as but not limited to chest pain, dyspnea, arrhythmia or edema are referred to a local cardiologist for cardiac evaluation such as (treadmill) ECG, cardiac enzymes and/or echocardiogram. Depending on the results of these evaluations, further diagnostic tests will be done as recommended by the cardiologist and subjects will be followed up at a frequency determined by the cardiologist. AESIs will be followed up until complete resolution or until the sequelae are stable and considered to be permanent.

[Figure 1](#) outlines the algorithm for assessment of cardiac events.

**Figure 1: Algorithm for Assessment of Cardiac Events**

\*At any protocol-scheduled ECG and/or troponin I abnormality, the algorithm will begin at this point.

### 8.2.8 Safety Laboratory Measurements

The intensity of laboratory / systemic quantitatively measured toxicities will be graded according to the toxicity scale in [Appendix I](#). These grading scales include the laboratory values determined with the routine safety parameters. In case of other laboratory values not included in the routine safety laboratory and not listed in [Appendix I](#), the National Cancer Institute Common Toxicity Criteria table, Version 4.3, published June 14, 2010 will be used for grading of laboratory toxicities.

Safety laboratory is determined at SCR, Visit 2 and Visit 4 and at any other visit(s) if clinically indicated. The safety laboratory measurements are performed at a central laboratory. Laboratory normal ranges are provided by the central laboratory and filed in the Investigator File. Safety laboratory parameters to be evaluated are:

Hematology:

Red blood cell count, hemoglobin, total and differential white blood cell count (WBC), platelet count

Serum chemistry:

Total bilirubin, AP, AST, ALT, serum creatinine (for calculation of CrCl at SCR), sodium, potassium, calcium, troponin I (troponin I mandatory at the SCR and Visit 2 and in addition at Visit 4 if clinically indicated).

Pregnancy test:

A  $\beta$ -human chorionic gonadotropin (HCG) pregnancy test will be conducted for all WOCBP at SCR, within 24 hours prior to each vaccination (Visits 1, 3) and at Visit 5 ( respectively the individual last active trial phase visit). At screening, a serum  $\beta$ -HCG pregnancy test will be performed; all other pregnancy tests will be conducted as urine  $\beta$ -HCG tests.

The following parameters will only be evaluated during SCR for assessment of inclusion / exclusion criteria:

Cholesterol: Total, HDL and LDL

### 8.2.9 Pregnancy

As per inclusion criteria, women of childbearing potential must have a negative serum pregnancy test at screening and a negative urine pregnancy test within 24 hours prior to each vaccination. In addition, they must have used an acceptable method of contraception for 30 days prior to the first vaccination, must agree to use an acceptable method of contraception during the trial, and must avoid becoming pregnant for at least 28 days after the last vaccination. Nevertheless, IMP exposed pregnancies cannot be excluded with certainty. Subjects who become pregnant prior to the first vaccination will be excluded from the trial and are regarded as screening failure. Subjects who become pregnant during the active trial period (up to and including one month [minimum 28 days] after receiving a dose of vaccine) must not receive additional doses of vaccine but may continue other trial procedures at the discretion of the investigator. All IMP exposed pregnancies should be followed up until delivery.

Subjects should be instructed to notify the investigator if it is determined after completion of the trial that they became pregnant either during the trial or within one month (minimum 28 days) after receiving the last vaccine dose.

